## Section 9 – Concomitant findings on admission

- ! Choledocholithiasis (Yes/Yes with common bile duct obstruction/No)
- ! Cholangitis (Yes/No)
- ERCP with sphincterotomy (Yes-within 24 hours/Yes within 24-48 hours/Yes within 48-72 hours/No)

## Section 10 – 30-day Morbidity

- ! Gastric outlet obstruction (Yes/No)
- ! Pseudocyst (Yes/No)
- ! Infected necrosis (Yes/No)
- ! Endoscopic drainage of pseudocyst/walled-off necrosis (Yes/No)
- ! CT-guided fine needle aspiration in case of infected pseudocyst/walled-off necrosis (Yes/No)
- ! Surgical necrosectomy (Yes-laparoscopic/Yes-open/No)
- ! Timing of surgical necrosectomy (< 2 weeks from the onset of symptoms/2-4 weeks)>4 weeks)
- ! Setting of surgical necrosectomy (Upfront/After failure of endoscopic necrosectomy/After failure of endoscopic and percutaneous necrosectomy)
- ! Cystogastrostomy (Yes-endoscopic/Yes-surgical/No)
- ! Abdominal compartment syndrome (Yes/No)
- ! Open abdomen (Yes/No)
- ! Timing of re-exploration (24-48 hours/48-72 hours/>72 hours)
- ! Bleeding (Yes/No)
- ! Bowel ischemia (Yes/No)

- ! Bowel fistula (Yes/No)
- ! Necrotizing cholecystitis (Yes/No)

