#### Primary objective

! To evaluate which items of the current AP guidelines, if disregarded, correlate with

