#### Secondary outcomes

- ! Early definitive treatment rate in 2019 vs. 2020: defined as treatment in accordance with the current guidelines (cholecystectomy or ERCP with endoscopic sphincterotomy during the same hospital admission or within 2 weeks of discharge)
- ! 30-day hospital readmission rate in 2019 vs. 2020: defined as hospital readmission within 30days from discharge for recurrent biliary AP while awaiting interval cholecystectomy, or due to post-cholecystectomy complications
- ! Predictive factors of morbidity and mortality in patients with biliary AP

The compliance of surgeons to the most up-to-date international guidelines on biliary AP will be assessed through the analysis of the following attitudes:

! Use of scoring systems for the diagnosis and severity grading of biliary AP

- ! Use of lipase dosage (for the diagnosis) and CRP (for the severity grading) during the diagnostic workup
- ! Use of Ultrasound scan, CT scan, MRCP, and endoscopic Ultrasound scan (EUS) in the correct way and timing
- ! Use of early ERCP and sphincterotomy in case of cholangitis and/or choledocholithiasis
- ! Use of percutaneous and/or endoscopic drainage in case of infected pseudocyst or necrosis
- ! Timing of surgical necrosectomy
- ! Timing of re-laparotomy in case of open abdomen strategies
- ! Use of prophylactic antibiotics/antifungals
- ! Use of somatostatin analogs
- ! Use of early enteral feeding
- ! Use of early definitive treatment strategies, including cholecystectomy and/or ERCP and sphincterotomy

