16. Enteral nutrition	! Enteral nutrition is recommended to prevent gut failure and infectious complications. Total parenteral nutrition (TPN) should be avoided but partial parenteral nutrition integration should be considered to reach caloric and protein requirements if enteral route is not completely tolerated. Both gastric and jejunal feeding can be delivered safely (1A).
17. Indications for emergent ERCP	
 
! Routine ERCP with acute gallstone pancreatitis is not indicated (grade 1A).
 
! ERCP in patients with acute gallstone pancreatitis and cholangitis is indicated (grade 1B).
 
! ERCP in acute gallstone pancreatitis with common bile duct obstruction is indicated (grade 2B).
 
! ERCP in patients with predicted severe acute gallstone pancreatitis without cholangitis or common bile duct obstruction cannot be
 

	recommended at this time (grade 2B).
18. Indications for percutaneous/endoscopi c drainage of pancreatic collections	
 
Clinical deterioration with signs or strong suspicion of infected necrotizing pancreatitis is an indication to perform intervention (percutaneous/endoscopic drainage)
 

	After 4 weeks after the onset of the disease:
	– On-going organ failure without sign of infected necrosis
	– On-going gastric outlet, biliary, or intestinal
	obstruction due to a large walled off necrotic
	collection – Disconnected duct syndrome
	- Symptomatic or growing pseudocyst
	After 8 weeks after the onset of the disease:
	- On-going pain and/or discomfort (grade 1C)
19. Indications for surgical intervention	! As a continuum in a step-up approach after percutaneous/endoscopic procedure with the same indications
	
 
Abdominal compartment syndrome
 
Acute on-going bleeding when endovascular approach is unsuccessful
 
Bowel ischaemia or acute necrotizing cholecystitis during acute pancreatitis
 
Bowel fistula extending into a peripancreatic collection (Grade 1C)
 

20. Timing of surgery	Postponing surgical interventions for more than 4 weeks after the onset of the disease results in less mortality (2B).

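### The drainage compliance item cannot be fully scored: the CRF records neither whether a pseudocyst was infected nor whether percutaneous drainage was done

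*Combined protocol and SAP*

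**What the plan says.** The primary objective is "To evaluate which items of the current AP guidelines, if disregarded, correlate with" negative clinical outcomes. One of the eleven practices listed under Secondary outcomes for judging compliance is "Use of percutaneous and/or endoscopic drainage in case of infected pseudocyst or necrosis". Infection decides who is eligible, and either route of drainage counts.

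The fields that bear on this are in CRF Section 10:

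- "Pseudocyst (Yes/No)", with no infection status;
- "Infected necrosis (Yes/No)", so infection is recorded for necrosis;
- "Endoscopic drainage of pseudocyst/walled-off necrosis (Yes/No)", which covers the endoscopic route only and any such collection, infected or not;
- "CT-guided fine needle aspiration in case of infected pseudocyst/walled-off necrosis (Yes/No)", the only place where an infected pseudocyst is mentioned;
- a cystogastrostomy field (endoscopic, surgical or no), again without infection status;
- the setting of surgical necrosectomy, where the option "After failure of endoscopic and percutaneous necrosectomy" is the only mention of a percutaneous procedure.

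Statistical analysis plans regression of morbidity and mortality on clinical attitudes and other variables. It gives no denominator for any item, no rule for scoring disregard and no covariate list.

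**The concern.** An item can be scored as followed or disregarded only if the data show who was eligible and what was done. Here both are incomplete. A pseudocyst marked yes may or may not be infected. A no in the endoscopic drainage field may mean no drainage or percutaneous drainage.

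The gap matters because infection is likely to drive both the decision to drain and the risk of death. The section on management of pancreatic necrosis gives mortality of up to 30% once a necrotic collection is infected. If uninfected pseudocysts are scored with the rest, the not-drained group gains low-risk patients and the drained group stays mostly infected. The odds ratio then partly measures infection, which was not collected for pseudocysts and so cannot be fully adjusted for.

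**Working it through.** **1. Can another field supply the infection status?** A yes for aspiration points to known or suspected infection. A no mixes uninfected collections with infected ones that were not aspirated. That mixture is to be expected: Table 1 item 8, item 15 of the Japanese guideline table and advice 3 of Table 5 all say aspiration is not routinely needed, although Table 2 item 5 recommends it for some patients with necrosis. Temperature and procalcitonin are taken on admission and are not specific to a collection. No field closes the gap.

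**2. Size if all pseudocysts are included.** The plan gives no figure for this item, so there is none to reproduce. Assumed, per 400 patients:

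- 20 with infected necrosis and 20 others with a pseudocyst, of which a share s = 10%, 20% or 30% is infected;
- drainage in 80% of infected and 20% of uninfected collections;
- mortality of 30% if infected (the document's upper figure, given for necrotic collections and extended here to pseudocysts) and 2% if not;
- no effect of drainage on death, and all drainage recorded.

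Infected I = 20 + 20s; uninfected U = 20(1 − s). Drained = 0.8I + 0.2U, with deaths 0.3(0.8I) + 0.02(0.2U). Undrained = 0.2I + 0.8U, with deaths 0.3(0.2I) + 0.02(0.8U).

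For s = 10%: I = 22 and U = 18. Drained = 17.6 + 3.6 = 21.2, with 5.28 + 0.072 = 5.352 deaths (25.2%). Undrained = 4.4 + 14.4 = 18.8, with 1.32 + 0.288 = 1.608 deaths (8.6%). Crude OR = (5.352 × 17.192)/(15.848 × 1.608) = 3.61.

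| s | Ineligible (U/40) | Apparent compliance (true 80%) | Mortality, drained vs not | Crude OR (true 1.0) | OR within pseudocyst stratum | Mantel-Haenszel OR |
|---|---|---|---|---|---|---|
| 10% | 45% | 53% | 25.2% vs 8.6% | 3.61 | 4.2 | 1.39 |
| 20% | 40% | 56% | 26.0% vs 9.6% | 3.29 | 5.0 | 1.67 |
| 30% | 35% | 59% | 26.7% vs 10.9% | 2.98 | 5.0 | 1.83 |

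The Mantel-Haenszel column adjusts for the recorded infected-necrosis field. For s = 10% the necrosis stratum contributes 4.8 × 2.8/20 = 0.672 to both numerator and denominator. The pseudocyst stratum contributes 0.552 × 14.392/20 = 0.397 and 4.648 × 0.408/20 = 0.095. The ratio is 1.069/0.767 = 1.39. Adjustment removes much of the bias but not all of it.

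**3. Does the result depend on there being no true effect?** A second set of assumptions has drainage in 70% of infected and 5-20% of uninfected collections, and uninfected mortality of 1-5%. The crude OR is then:

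| Infected mortality, drained vs not | True OR | 20% uninfected | 50% uninfected | 80% uninfected |
|---|---|---|---|---|
| 30% vs 30% | 1.00 | 1.58-2.02 | 2.41-4.51 | 2.60-9.56 |
| 25% vs 40% | 0.50 | 0.88-1.11 | 1.52-2.64 | 1.92-6.11 |
| 15% vs 50% | 0.18 | 0.36-0.44 | 0.70-1.12 | 1.10-2.81 |

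The shift is against drainage in every cell, but it does not always pass 1.

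**4. The missing percutaneous field.** Take 50% uninfected, 5% of them drained, 3% uninfected mortality and 30% infected mortality. If all drainage is recorded, mortality is 28.2% vs 9.5% and the OR is 3.75. If half of the drained infected cases were percutaneous and are coded as not drained, it is 26.6% vs 14.0% and the OR is 2.23. If the percutaneous cases are also sicker (45% mortality against 15% for endoscopic, averaging the same 30%), it is 13.5% vs 17.3% and the OR is 0.75. The two gaps can pull in opposite directions.

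**The case against.** The strongest reply is that nothing obliges the analyst to count every pseudocyst. A reader might infer that uninfected pseudocysts will enter the denominator, but the documents define none. Restricting the item to recorded infected necrosis removes this bias: under the assumptions of step 2, mortality is 30% in both groups and the OR is 1.00. That stands. The price is the infected pseudocysts, which are 2 of 22 to 6 of 26 eligible patients (9-23%). The restriction also drops part of the item's own wording and is not prespecified.

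A reader might also infer that drainage will look lethal. The documents do not support that. Most inputs are assumed, the 30% is an upper figure for necrotic collections only, and a truly protective effect can leave the OR below 1. The illustration holds only about 7 to 8 deaths in 40 patients, so the approximate 95% interval for the crude OR runs from about 0.5 to 18-24. The crude figure also assumes no adjustment, whereas regression is planned, though without named covariates.

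Finally, a reader might take leaving an uninfected pseudocyst alone as always in line with the guidelines. Table 1 item 18 lists "Symptomatic or growing pseudocyst" among the indications after 4 weeks, without requiring infection. The CRF records neither symptoms nor growth of the pseudocyst nor the timing of drainage, so agreement with that row cannot be judged either way.

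**Conclusion.** The point holds as a data gap. Eligibility cannot be determined for pseudocysts, and compliance cannot be determined for patients drained percutaneously. If all pseudocysts are included, compliance is understated and the association with death moves against drainage. With no true effect and the assumptions of step 2, the crude OR is about 3.0-3.6, or about 1.4-1.8 after adjustment for infected necrosis. These figures show direction and rough scale and do not forecast the result. The net direction is not settled once percutaneous drainage is miscoded as well. The problem is confined to one of eleven listed practices, but that practice bears on the primary objective and the data cannot be recovered at analysis, so it should be corrected.

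**What to change.** - Recode the pseudocyst field to three answers: no; yes, no infection; yes, infected or strongly suspected.
- Add a percutaneous drainage field (yes/no).
- State in the analysis section that the denominator is patients with infected pseudocyst or infected necrosis.
- Report drainage of uninfected pseudocysts descriptively as a separate item, scored neither as compliance nor as disregard.

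If the fields cannot be added, restrict the item to patients with infected necrosis recorded as yes, relabel it as endoscopic drainage, and state that infected pseudocysts and percutaneous drainage are not captured.

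The cost is one recoded field, one new field, a few sentences and slightly more chart abstraction. The study is retrospective, so the information can be taken from records where it was charted. Fewer patients will contribute to the item.

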#### Background

Acute pancreatitis (AP) is an inflammatory disease of the pancreas, most commonly caused by gallstones or excessive alcohol use. It represents a management challenge and a significant healthcare burden. The incidence of AP ranges globally from 5 to 30 cases per 100.000 inhabitants/year, and there is evidence that the incidence has been rising in recent years. The overall case-fatality rate for AP is roughly 5%, and it is expectedly higher for more severe stages of the disease [1, 2]. In most cases (80%), the outcome of AP is rapidly favorable [3]. However, acute necrotizing pancreatitis (ANP) may develop in up to 20% of cases and is associated with significant rates of early organ failure (38%), needing some surgical/endoscopic intervention (38%), and death (15%) [4].

In the United States, AP is a leading cause of inpatient care among gastrointestinal conditions: more than 270.000 patients are hospitalized for AP annually, at an aggregate cost of over 2.5 billion dollars per year [5]. In Europe, the UK incidence of AP is estimated as 15-42 cases per 100.000/year and is rising by 2.7% each year [6].

Several scientific societies published their clinical practice guidelines making recommendations on the management of AP [7] (Table\_1-4). These guidelines' main topics are the diagnosis, antibiotic treatment, management in the intensive care unit, surgical and operative management, and open abdomen management.

Audits about biliary AP have been performed in Italy, Germany, France, and England, with quite disappointing results [8-11]. Indeed, in these audits, the treatment of biliary AP differed substantially from the recommendations. For example, less than 15% of the responders stated that they strictly followed all recommendations included in the guidelines in Germany, and 25.8% of patients did not receive definitive treatment for biliary AP within one year in the UK [12].

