# negative clinical outcomes according to the different clinical presentations of the disease

#### Secondary objectives

- ! To assess the compliance of surgeons worldwide to the most up-to-date international guidelines on biliary AP
- ! To evaluate the medical and surgical practice in the management of biliary AP during the nonpandemic (2019) and pandemic Covid-19 periods (2020)
- ! To investigate outcomes of patients with biliary AP treatment during the two study periods

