#### **Primary outcomes**

- ! 30-day mortality: assessed by the number of AP patients with biliary etiology deceased during the non-pandemic period (2019) and the Covid-19 pandemic period (2020)
- ! 30-day morbidity: assessed by the number of AP patients with biliary etiology who experienced any type of AP-related complication within 30-days from the hospital admission during the non-pandemic period (2019) and the Covid-19 pandemic period (2020)

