## Table\_5: Statement and Recommendations from the AGA guidelines for the management of

## patients with pancreatic necrosis

BEST PRACTICE ADVICE 1	Pancreatic necrosis is associated with substantial morbidity and mortality and optimal management requires a multidisciplinary approach, including gastroenterologists, surgeons, interventional radiologists, and specialists in critical care medicine, infectious disease, and nutrition. In situations where clinical expertise may be limited, consideration should be given to transferring patients with significant pancreatic necrosis to an appropriate tertiary-care center.
BEST PRACTICE ADVICE 2	Antimicrobial therapy is best indicated for culture-proven infection in pancreatic necrosis or when infection is strongly suspected (ie, gas in the collection, bacteremia, sepsis, or clinical deterioration). Routine use of prophylactic antibiotics to prevent infection of sterile necrosis is not recommended.
BEST PRACTICE ADVICE 3	When infected necrosis is suspected, broad-spectrum intravenous antibiotics with ability to penetrate pancreatic necrosis should be favored (eg, carbapenems, quinolones, and metronidazole). Routine use of antifungal agents is not recommended. Computed tomography–guided fine-needle aspiration for Gram stain and cultures is unnecessary in the majority of cases.
BEST PRACTICE ADVICE 4	In patients with pancreatic necrosis, enteral feeding should be initiated early to decrease the risk of infected necrosis. A trial of oral nutrition is recommended immediately in patients in whom there is absence of nausea and vomiting and no signs of severe ileus or gastrointestinal luminal obstruction. When oral nutrition is not feasible, enteral nutrition by either nasogastric/ duodenal or nasojejunal tube should be initiated as soon as possible. Total parenteral nutrition should be considered only in cases where oral or enteral feeds are not feasible or tolerated.
BEST PRACTICE ADVICE 5	Drainage and/or debridement of pancreatic necrosis is indicated in patients with infected necrosis. Drainage and/or debridement may be required in patients with sterile pancreatic necrosis and persistent unwellness marked by abdominal pain, nausea, vomiting, and nutritional failure or with associated complications, including gastrointestinal luminal obstruction; biliary obstruction; recurrent acute pancreatitis; fistulas; or persistent systemic inflammatory response syndrome.

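### The CRF has no field for pancreatic necrosis regardless of infection, so conservatively managed sterile necrosis can leave no trace in 30-day morbidity and the necrotizing subgroup is only partly identifiable

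*Combined protocol and SAP*

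**What the plan says.** - **Primary outcomes.** 30-day morbidity is the number of patients who "experienced any type of AP-related complication within 30-days from the hospital admission". No rule says which CRF rows make up this outcome.
- **Primary objective.** Disregarded guideline items are to be related to "negative clinical outcomes according to the different clinical presentations of the disease". The presentations are not listed.
- **Background.** It states that "acute necrotizing pancreatitis (ANP) may develop in up to 20% of cases", and that 38% of these patients need a surgical or endoscopic intervention and 15% die. The section on management of pancreatic necrosis describes these patients as a subgroup with dedicated guidance, set out in Table 5. Best Practice Advice 2 in that table reads: "Routine use of prophylactic antibiotics to prevent infection of sterile necrosis is not recommended".
- **CRF Section 10 (30-day morbidity).** The one row for necrosis as a finding is "Infected necrosis (Yes/No". Necrosis can also show indirectly through "Endoscopic drainage of pseudocyst/walled-off necrosis (Yes/No", through "Surgical necrosectomy (Yes-laparoscopic/Yes-open/No" with its timing and setting rows, and through the cystogastrostomy row. None of these carries an infection condition. The aspiration row, "CT-guided fine needle aspiration in case of infected pseudocyst/walled-off necrosis (Yes/No", is worded for infected collections.
- **CRF Section 7 (imaging).** Modality and timing only.
- **CRF Section 4 (scores).** Revised Atlanta grade in three levels, and organ failure by system. Neither names necrosis.

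**The concern.** The morbidity outcome is defined broadly, but the form that feeds it has a gap at the complication that the Background presents as the serious form of the disease. A No in the infected-necrosis row can mean no necrosis, sterile necrosis, or no scan able to show it. Section 10 does count a pseudocyst without asking about infection, so sterile necrosis is not left out by a general rule that only infected collections matter.

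Two things are at stake. The first is a primary outcome: 30-day morbidity can be undercounted. The second is the primary objective: if necrotizing disease is one of the presentations meant, patients who have it cannot be reliably separated from those who do not. Some tabled advice is specific to necrosis, for example on antibiotic prophylaxis and on early feeding (Table 5, Best Practice Advice 2 and 4), and adherence to it cannot be judged in its target group.

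**Working it through.** The plan states no figure on this point, so there is none to reproduce. The check has two parts.

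**1. Can sterile necrosis be recovered from the CRF?** Take a patient with sterile necrosis on CT, treated conservatively, with no other complication.

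- Section 7 shows that a CT was done and when, not what it found.
- Section 4 gives a severity grade and organ failure. Neither separates necrotizing from non-necrotizing disease.
- In Section 10, infected necrosis is No, and so are endoscopic drainage, necrosectomy, cystogastrostomy and every other listed event.

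If morbidity is built from Section 10, this patient counts as free of it. If the same patient has endoscopic drainage or necrosectomy, a row is positive. A positive drainage row still does not prove necrosis, because it is shared with pseudocyst.

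**2. How many patients could this be?**

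Inputs:

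- Necrosis in up to 20% of cases (Background; all acute pancreatitis, not biliary only). Lower values of 5%, 10% and 15% are assumed.
- Intervention in 38% of necrotizing cases (Background), so 1 − 0.38 = 0.62 have none.
- Minimum cohort 2 × 200 = 400 (Sample size), used only to scale.

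Formula: affected share ≤ necrosis share × 0.62.

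| Necrosis share | × 0.62 | Of 400 |
|---|---|---|
| 20% (Background maximum) | 12.4% | 49.6 |
| 15% (assumed) | 9.3% | 37.2 |
| 10% (assumed) | 6.2% | 24.8 |
| 5% (assumed) | 3.1% | 12.4 |

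The documents give no share of necrosis that becomes infected. Let that share be i, assumed between 20% and 50%. Patients who are both sterile and without intervention cannot exceed either group alone, so at 20% necrosis the bound is 20% × min(1 − i, 0.62):

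- i = 0.20: 20% × min(0.80, 0.62) = 12.4%.
- i = 0.50: 20% × min(0.50, 0.62) = 10.0%, or 40 of 400.

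Patients with another Section 10 event still have to be subtracted. The documents do not give that overlap, so no lower limit can be calculated.

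**The case against.** The strongest reply is that the form is less blind than it looks. Three parts of that reply stand.

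- A reader might infer that the CRF captures necrosis only when it is infected. The drainage and necrosectomy rows show otherwise.
- A reader might infer that every patient with sterile necrosis is stored as free of morbidity. That holds only without an intervention or another listed event, and only if morbidity is derived from Section 10 alone, which the plan does not say. Organ failure and ICU admission are recorded elsewhere.
- A reader might infer that the primary objective cannot be met. The protocol never names necrotizing disease as one of its presentations, and the CRF does support analysis by severity, cholangitis, duct obstruction and organ failure. The compliance list under Secondary outcomes names prophylactic antibiotics without a necrosis condition, and Table 1 advises on routine prophylaxis in acute pancreatitis generally, so that item can be assessed without a necrosis field.

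The indirect rows do not close the gap. They show only treated cases, the drainage row mixes two conditions, and Section 10 has no row for percutaneous drainage. In Table 1, the listed indications for draining collections without infected necrosis start 4 or 8 weeks after onset, near or beyond a 30-day window.

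A second objection concerns the remedy. Sterile necrosis is seen only in patients who are scanned, and CT use is itself a compliance item that may differ between 2019 and 2020. Counting it ties the outcome to an exposure under study. This is correct, but the existing pseudocyst row has the same dependence. It calls for a sensitivity analysis and does not justify leaving the finding unrecorded.

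**Conclusion.** The point holds in this form: the CRF has no row for pancreatic or peripancreatic necrosis regardless of infection, so sterile necrosis with no drainage, necrosectomy or other listed event is missing from the 30-day morbidity section. The necrotizing subgroup is only partly identifiable. Treating that subgroup as one of the intended presentations is an inference from the space that the protocol and Table 5 give it.

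The ceiling is 12.4%, about 50 of 400, on the Background's figures, and 3.1–9.3% at an assumed 5–15% necrosis. It assumes that every intervention in the 38% is recorded in Section 10; the protocol does not say how many of them fall within 30 days. The true number is lower to the extent that untreated patients have infected necrosis or another event.

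Two stronger readings are not supported. With 20% infected, 400 × 0.20 × 0.80 = 64 patients have sterile necrosis, and a reader might take 64 as the number missed. But of 80 necrotizing cases, 80 × 0.38 = 30.4 have an intervention, which leaves 49.6, so at least 14.4 of the 64 would appear in a procedure row. A reader might also infer that any association between prophylaxis and infected necrosis merely reflects who had necrosis. The Statistical analysis section plans models for morbidity and mortality only, so that comparison is hypothetical.

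**What to change.** - Recode the Section 10 row as *Pancreatic/peripancreatic necrosis: none on CT/MRI; present, not infected; present, infected; no CT or MRI*.
- State which CRF rows define 30-day morbidity, and that necrosis of either kind is included.
- Report necrotizing versus non-necrotizing disease as a presentation subgroup among patients who had CT or MRI.
- Report 30-day morbidity without sterile necrosis as a sensitivity analysis, because detection depends on CT use and that may differ between the two years.

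The cost is one extra item per patient, read from existing imaging reports, plus a few lines in the analysis section. If records have already been entered, centres would have to return to those reports. The reported morbidity rate will be higher, and part of it will depend on who was scanned.
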